1.0 INTRODUCTION

Prior to surgery or other invasive procedures, skin must be treated with a topical antimicrobial product to minimize the risk of nosocomial infection by reducing the number of microorganisms on the skin. The Food and Drug Administration (FDA) Tentative Final Monograph (TFM) for *Topical Antimicrobial Drug Products for Overthe-Counter Human Use; Tentative Final Monograph for Healthcare Antiseptic Drug Products* (Vol. 59, No. 116, June 17, 1994) describes *in-vivo* procedures for evaluating this type of product, as well as expected performance criteria: $\geq 2 \log_{10}$ reduction from baseline bacterial counts on abdominal sites for samples taken 10 minutes post product treatment, $\geq 3 \log_{10}$ reduction from baseline bacterial counts on inguinal sites for samples taken 10 minutes post product treatment, and $> 0 \log_{10}$ reduction from baseline bacterial counts on abdominal and groin sites for samples taken 6 hours post product treatment

Octenidine dihydrochloride (OCT) is an antiseptic agent that has a broad spectrum of

activity against bacteria, yeast, and fungi. Its activity is persistent for hours to days after application, rendering it a suitable antimicrobial product to develop for use as a skin antiseptic.

2.0 OBJECTIVE

The objective of this study is to compare the immediate and persistent antimicrobial properties of thermally treated polyester cloth impregnated with 0.4% w/v octenidine dihydrochloride in clear aqueous solution, thermally treated polyester cloth impregnated with vehicle formulation, and the FDA-approved Sage 2% Chlorhexidine Gluconate Cloth to the log reduction and response rate standards set forth in the Food and Drug Administration Tentative Final Monograph (TFM) for *Effectiveness Testing of a Patient Preoperative Skin Preparation*. Testing will be performed according to the procedures outlined in the Food and Drug Administration Tentative Final Monograph (TFM) for *Effectiveness Testing of a Patient Preoperative Skin Preparation* (FR 59:116, 17 June 94, pp. 31450-31452). The test methods for this evaluation will be based on ASTM Standard Test Method E1173-15, *Eevaluation of Preoperative, Precatheterization, or Preinjection Skin Preparations* and the test criteria from the 1994 FDA TFM.

3.0 **SPONSOR**

[figure not shown]
BD

[name] [name]

[contact]

INVESTIGATIVE ORGANIZATION AND PERSONNEL 4.0

BioScience Laboratories, Inc. [name] [name]

Principal Investigator: [name]

Subinvestigators: [name], [name], and [name], CCRP

Study Statistician:

Director of Quality Assurance:

Consulting Physician/Medical Expert:

the Subject Subject Recruitment and Consenting, IRB Coordination:

Recruitment Department or designee

Sponsor Contact(s):

Sponsor Medical Monitor:

Study Monitor:

Name of the IRB 4.1

Gallatin Institutional Review Board (GIRB)

[name]

[name]

DHHS Number: IRB00005939

ROLES AND RESPONSIBILITIES 5.0

6.0 CLINICAL RESEARCH STANDARDS

The clinical investigation, including the informed consent, will be approved by the Gallatin Institutional Review Board (GIRB) in accordance with Title 21 of the Code of Federal Regulations, Parts 50, 56, 58, 312, and 314, and in accordance with the International Conference on Harmonisation (ICH) guidelines. The written approval of the Board will be obtained prior to the initiation of the study.

The study will be conducted in accordance with Good Clinical Practice regulations, Good Laboratory Practice regulations, the Standard Operating Procedures of BioScience Laboratories, Inc., the study protocol, any protocol amendments, and the regulatory

requirements of the United States Food and Drug Administration (FDA) and ICH.

7.0 SCOPE

The objective of this study is to compare the immediate and persistent antimicrobial properties of thermally treated polyester cloth impregnated with 0.4% w/v octenidine dihydrochloride in clear aqueous solution, thermally treated polyester cloth impregnated with Vehicle formulation, and the FDA-approved Sage 2% Chlorhexidine Gluconate Cloth against the log reduction and response rate standards set forth in the Food and Drug Administration Tentative Final Monograph (TFM) for *Effectiveness Testing of a Patient Preoperative Skin Preparation*. Testing will be performed according to the procedures outlined in the Food and Drug Administration Tentative Final Monograph (TFM) for *Effectiveness Testing of a Patient Preoperative Skin Preparation* (FR 59:116, 17 June 94, pp. 31450-31452). The test methods for this evaluation will be based on ASTM E1173-15, , *Standard Test Method for Evaluation of Preoperative, Precatheterization, or Preinjection Skin Preparations* and the test criteria from the 1994 FDA TFM.

A sufficient number of male and female, overtly healthy, volunteer subjects at least 18 years of age, will be enrolled in the screening phase to ensure that the total numbers of evaluable samples collected from groin and abdominal regions meet or exceed 48 evaluable test sites from Investigational Product and Active Control arms and 16 evaluable test sites from Vehicle Control arm (minimum of 112 each for groin and abdominal regions). Subjects must satisfy all Screening Day and Treatment Day Inclusion/Exclusion Criteria prior to screening sample collection and Treatment Day procedures. If the required numbers of subjects do not qualify from the initial screening group, additional volunteers will be recruited.

Following a 14- day restriction period, subjects with resident bacterial flora that meet the specified criteria will be eligible to proceed to the treatment phase of testing. Specific baseline criteria for subjects will be $\geq 3.11 \log_{10}$ CFU/cm² from the skin of the abdomen and $\geq 5.5 \log_{10}$ CFU/cm² from the skin of the inguen. Evaluations will consist of samples collected at baseline, 10 minutes \pm 30 seconds post-treatment, and at 6 hours \pm 30 minutes post-treatment. All plating for this study will be conducted in duplicate with the pour-plating technique and incubated at 30 ± 2 °C for 72 hours \pm 4 hours. The left and right abdominal test sites will be 5" × 5" areas of skin. The abdominal sampling sites will not include skin that shows evidence of the subjects clothing waistband. The test sites on the left and right inguina will be 2" × 5" areas of skin that appear to be similar in condition. Subjects passing into the treatment phase of testing will be sampled for baseline microbial populations on randomly assigned sites of each abdominal and inguinal test area.

7.1 Primary Analysis

A modified intent to treat (mITT) data set will be used for efficacy analyses. Inclusion for the mITT data set is evaluated for each body area (left and right for the groin and abdomen). For each body area, if the treatment day baseline bacterial count requirements are in the range of 3.11 to 5.50 log₁₀/cm², inclusive, on the abdomen and 5.50 to 7.50 log₁₀/cm², inclusive, on the groin, then the data from that body area are included in the mITT data. Efficacy analyses will also be conducted on the Per Protocol data set as supportive analyses when Per Protocol data are different from mITT data.

- For responder rate, missing data will be imputed as non-responders in the mITT data, while in the Per Protocol data, missing data will not be imputed and will be excluded from the responder rate Per Protocol analyses.
- For log reduction, missing data will not be imputed for either mITT data or Per Protocol data and will be excluded from log reduction analyses.

Log₁₀ reductions for the analysis of the efficacy will be calculated by subtracting the post-test material application log₁₀ recovery from the Treatment Day baseline log₁₀ recovery. Log₁₀ reductions will be calculated for all study materials for both the groin and the abdomen at both the 10 minute and 6 hour sample times.

The primary measure of antimicrobial efficacy is the responder rate. Responder status is calculated separately for each treatment, body area (abdomen and groin), and each post-application sample time. At the 10-minute sample time a subject is defined as a responder for the groin if they show at least a $3 \log_{10}$ reduction from baseline skin flora counts; a subject is defined as a responder for the abdomen if they show at least a $2 \log_{10}$ reduction from baseline skin flora counts. At the 6-hour sample time a subject is defined as a responder if they have a microbial mean \log_{10} reduction from baseline that is greater than 0. The primary efficacy target is to show a 70% responder rate for each body area and post-application sample time for the Investigational Product.

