13.5 Baseline Screening Procedures

Baseline-screening samples will be taken on the day following the-14 day pre-test period. Subjects will not shower at least 72 hours prior to being sampled. Subjects will don a disposable undergarment prior to baseline screening procedures and will be examined physically to ensure that there is no evidence of injury, dermatosis, folliculitis, or dermatitis present at the sampling sites (Section 14.2). A subject will be dismissed from the study if skin irritation score of 1 is observed on the test sites. If the subject continues to meet the qualification criteria, they will be sampled using the Cylinder Sampling (Scrub Cup) Technique (Section 13.7) at the center of the sampling areas on the skin of the inguina and abdomen (Appendix 2). There will be a minimum of 72 hours between the time the screening period ends and the experimental period begins. Based upon adequate screening microbial counts, subjects will be eligible to continue into the treatment phase of the study. Subjects may qualify on one or two anatomical site(s) and be admitted into testing for those anatomical site(s) only, although if more subjects qualify for treatment than can be treated in a given time period, preferential admittance into the treatment phase will be given to subjects qualifying in both the abdominal and inguinal test areas.

Baseline criteria for qualification for the test period are $\geq 3.11 \log_{10} \text{ CFU/cm}^2$ from the skin of the abdomen, and/or $\geq 5.50 \log_{10} \text{ CFU/cm}^2$ from the skin of the groin.

There will be a minimum of 72 hours between baseline screening procedures and treatment day procedures. Based upon achieving adequate baseline screening microbial counts, subjects will be eligible to continue to treatment day procedures.

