13.10 Data Handling

The estimated log₁₀ number of viable microorganisms per cm² recovered from each sample site will be designated the "R-value."

To convert the volumetric measure of the sample into the number of colony-forming units per square centimeter (cm²), the following formula will be employed:

$$R = \log_{10} \left[\frac{F\left(\frac{\sum c_i}{n}\right) 10^{-D}}{A} \right]$$

where:

R = the average colony-forming unit count in log_{10} scale per cm² of sampling surface

F = total number of mL of stripping fluid added to the sampling cylinder; in thisstudy, F = 6 mL for all samples

 $\frac{\sum c_i}{n}$ = average of the duplicate colony counts used for each sample collected

D =dilution factor of the plate counts

A = inside area of the cylinder in cm²; in this study, $A = 3.46 \text{ cm}^2$ (2.1 cm i.d.)

NOTE: The reason that a log₁₀ transformation will be performed on the collected data is to obtain a linear scale. A linear scale, more appropriately a log₁₀ linear scale, is a basic requirement of the statistical models used in this study.

If colonies on one of the plates are uncountable, the count from the remaining plate will be used. In order to avoid potential calculation problems due to taking the logarithm of zero, counts of zero will be considered 1 for further calculations.

Data collected from subjects with low test-day baseline counts on an anatomical test site ($< 3.11 \log_{10} \text{CFU/cm}^2$ from the skin of the abdomen, or $< 5.50 \log_{10} \text{CFU/cm}^2$ on the skin on the inguen) will not be used in the mITT Efficacy Analyses (Section 15.0).

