15.1 Primary Analysis

An analysis of variance (ANOVA) of the baseline log_{10} CFU/cm² values will be performed to determine whether the randomization produced treatment arms with similar baseline CFU/cm² values.

Log₁₀ reductions for the analysis of the efficacy and comparison endpoints will be calculated by subtracting the post-test material application log₁₀ recovery from the Treatment Day baseline log₁₀ recovery. Log₁₀ reductions will be calculated for all study materials for both the groin and the abdomen at the 10 minute and 6 hour sample times.

Responder rates will be calculated by converting each \log_{10} CFU/cm² reduction to a binary (yes or no) success measure. Success at 10 minutes is defined as achieving a 2 \log_{10} per cm² reduction of skin flora on the sebaceous-poor site (abdomen) and a 3 \log_{10} per cm² reduction of skin flora on the sebaceous-rich site (groin). Success at 6 hours is defined as having skin flora counts that are less than the baseline skin flora counts. Responder rates and 95% confidence intervals will be summarized for each product tested, grouped by anatomical site and each post-application time point (10 minutes and 6 hours).

The primary purpose of the study is to compare antimicrobial activity of the Investigational Product to the responder rate standards according to the FDA TFM. Investigational Product, Vehicle Control and Active Control will be compared to the efficacy standard of a 70% response rate at 10 minutes and 6 hours. It is expected that the mean responder rates will meet that standard, but since this is a Phase 2 study to inform design of future Phase 3 pivotal efficacy studies and is not designed to provide statistically powered evidence of efficacy, the confidence intervals may not lie entirely above 70%.

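### The mITT window selects sites on the same Treatment Day reading that the log reduction is measured from, so fixed-target results carry a regression-to-the-mean bias of unknown sign

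*Combined protocol and SAP*

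**What the plan says.** Section 7.1 (repeated in 15.0) decides mITT membership site by site. A site is in "if the treatment day baseline bacterial count requirements are in the range of 3.11 to 5.50 log₁₀/cm², inclusive, on the abdomen", and for the groin if the count lies between 5.50 and 7.50; "then the data from that body area are included in the mITT data". The window has two sides. Section 13.10 repeats only the lower cut, for "Data collected from subjects with low test-day baseline counts on an anatomical test site".

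The outcome uses the same reading. Log reductions come from "subtracting the post-test material application log₁₀ recovery from the Treatment Day baseline log₁₀ recovery", and section 15.1 turns each reduction into responder or non-responder.

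The results are judged against fixed standards. All three products "will be compared to the efficacy standard of a 70% response rate at 10 minutes and 6 hours" (15.1). The secondary targets for the Investigational Product are mean reductions of at least 3 (groin) and at least 2 (abdomen) at 10 minutes, and above 0 at 6 hours (7.2, 15.2).

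A separate count qualifies the site beforehand. Section 11.3 requires Screening Day counts at or above the same lower thresholds on both sides, with no upper limit, and 13.5 adds: "There will be a minimum of 72 hours between baseline screening procedures and treatment day procedures".

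The ITT set is for safety only. The Per Protocol set is supportive and is analysed only where it differs from the mITT. The supplied text describes no efficacy analysis without the window and no baseline adjustment. Section 15.0 leaves details to a separate SAP whose text is not supplied.

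**The concern.** Each time point is one cup sample from its own quarter of the site (13.3), so the Treatment Day baseline is the site's level plus sampling error. The lower cut removes sites that read low by chance and keeps those that read high by chance. The upper cut does the reverse. Whatever average error is left among the retained baselines passes straight into baseline minus post-treatment count, even for a product that does nothing.

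The window is the same in every arm, so differences in mean reduction between products are largely protected. A comparison with 70%, or with a mean of 3, 2 or 0, has no such protection. Section 15.1 expects the responder rates to reach 70% while accepting that the confidence intervals may not, so the point estimate carries the conclusion. Section 7.4 says the study informs Phase 3 design, so a shifted rate would be carried forward.

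**Working it through.** **Figures that can be reproduced.** The pairings in 13.3 give 40 + 8 = 48 sites for A, 40 + 8 = 48 for B and 8 + 8 = 16 for C, 112 in all from 56 subjects, as stated. There is no power calculation to reproduce. Reaching 70% of 48 needs 0.70 × 48 = 33.6, so 34 sites.

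**Assumed inputs, not in the documents.** Population mean m; between-site SD sb of 0.5–0.7; reading SD sw of 0.3–0.5 (the part of the error not shared by the baseline and post-treatment samples); product effect independent of baseline level.

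**Mechanism in closed form, ignoring screening.** With s = √(sb² + sw²), a = (L − m)/s and b = (U − m)/s for window L to U, the bias in mean log reduction is

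(sw²/s) × [φ(a) − φ(b)] / [Φ(b) − Φ(a)].

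For the groin (L = 5.50, U = 7.50) with sb = sw = 0.5, s = 0.707 and sw²/s = 0.354:

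- m = 5.5: a = 0, b = 2.83; 0.354 × (0.399 − 0.007)/0.498 = +0.28.
- m = 6.5: a = −1.41, b = 1.41; the two terms cancel, giving 0.
- m = 7.0: a = −2.12, b = 0.71; 0.354 × (0.042 − 0.311)/0.743 = −0.13.

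Screening on earlier, independent readings thins out the low sites. In simulation these three values become +0.16, −0.02 and −0.14. Screening lessens the upward bias but does not remove it.

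**Simulation of the plan as written.** Both sides must pass screening at the lower threshold on independent readings (assumed left–right correlation of true levels 0.8); then the two-sided mITT window is applied to the Treatment Day reading. Inert reduction = e_base − e_post. For the 10-minute case the product effect has SD 0.6 and a mean that makes the unfiltered responder rate 65%. The counting floor is left out.

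| Population mean relative to lower threshold | Inert product, 6-hour rate (unfiltered 50%) | 10-minute rate (unfiltered 65%) |
|---|---|---|
| 0.3 below to 0.5 above | 51–64% | 66–75% |
| about 0.75–1.0 above | about 50% | about 65% |
| 1.6 above | 41–48% | 59–64% |

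Keeping all screen-qualified sites returns the unfiltered rates.

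**A second set of scenarios** (true rate 70%, product-effect SD 0.5, reading SD up to 0.7) gives the shift in mean log reduction as well:

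| Region and m | Bias in mean (log10) | Rate read in mITT |
|---|---|---|
| Abdomen 3.1 | +0.06 to +0.21 | 73.6–78.0% |
| Abdomen 4.3 (centre) | −0.05 to 0.00 | 69.6–70.2% |
| Abdomen 4.8 | −0.18 to −0.03 | 65.2–68.5% |
| Groin 5.5 | +0.06 to +0.17 | 73.5–77.5% |
| Groin 6.5 (centre) | −0.08 to −0.01 | 68.9–69.9% |
| Groin 7.0 | −0.23 to −0.05 | 63.8–67.4% |

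Selection on screening alone gave 69.9–70.1%.

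**What a shift does to the 70% target.** By the exact binomial, the chance of at least 34 of 48 is 8% at a rate of 60%, 25% at 65%, 52% at 70% and 80% at 75%.

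**The case against.** A reader might infer that the filter inflates every responder rate and always favours passing. The documents do not support that. The window has upper bounds of 5.50 and 7.50, which drop sites that read high by chance, and no baseline mean or SD is given to say which cut dominates. Screening has only a lower limit, 13.10 names only low counts, and section 12.0 allows a second attempt at the baseline count. These show that the sponsor foresaw low counts. They do not show where the baselines will lie.

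It can also be said that this is an unpowered Phase 2 study with a descriptive target, that the Vehicle Control passes through the same filter and would show a shared shift, and that counting missing results as non-responders lowers the mITT rate. Each is partly right. The binomial chances above describe how easily the point target is reached, not a formal test. The Vehicle Control has only 16 sites per region, too few to measure a shift of a few points. The missing-data rule may work against an upward bias, but it is unrelated to it in size and would add to a downward one. None of this removes the bias from the fixed-target comparisons.

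**Conclusion.** The point holds for the comparisons with fixed targets, and its direction is open. The mITT responder rates and mean reductions carry a regression-to-the-mean bias whose sign depends on where baselines fall in the window. Over the scenarios examined it can move a responder rate by up to about 14 points upward (an inert product at 6 hours, 50% read as 64%) or about 9 points downward (50% read as 41%). It is about zero towards the middle of the window. These sizes rest on assumed SDs, normal errors, screening errors independent of Treatment Day errors, and a product effect that does not depend on baseline level. A rate already close to 100% can hardly move. Differences in mean reduction between products are largely unaffected. That no unfiltered efficacy analysis is planned can be verified only for the supplied text.

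**What to change.** In 7.1 and 15.1, add a supportive analysis of responder rates and mean log reductions on every treated site that met the Screening Day criterion, whatever its Treatment Day count. Report it beside the mITT, with the number of sites excluded at the lower and at the upper bound by product and region, and interpret the fixed-target results in the light of any difference. The mITT can stay primary, and no rule that both sets must meet a target is needed in an unpowered Phase 2 study.

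The cost is one extra set of tables and a paragraph, with no new data. One drawback should be stated. Zero counts are set to 1, so the lowest possible value is log10(6 × 1/3.46) = 0.24, and an abdominal site whose baseline is below 0.24 + 2 = 2.24 cannot show a 2-log drop. A few such sites may enter the added analysis and lower its 10-minute abdominal rate slightly (by about 2 points at most in simulation).

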13.3 Randomization

Subjects will be randomized to treatment using the following block design:

Treatment Balance

Each subject will receive two different treatments, one on the right side of the body and one on the left. This means there are three possible combinations of treatments (assuming A and B are either Investigational Product or Active Control; C is Vehicle Control):

- A and B
- A and C
- B and C

The treatment assignments will be balanced such that the number of readings per anatomical site matches the calculated requirements. The Investigational Product and Active Control will be applied to an equal number of anatomical sites. The Vehicle Control will be compared against each active substance an equal number of times. The Vehicle Control will be applied to the number of anatomical sites necessary to generate a baseline for comparison to the active substances.

A minimum of 56 evaluable subjects will be required to achieve a total of at least 112 test sites for groin and abdominal regions. Out of the minimum 56 evaluable subjects, 40 evaluable subjects will receive treatments from both A and B, 8 evaluable subjects will receive treatments from both A and C and 8 evaluable subjects will receive treatments from both B and C to achieve 48 evaluable test sites from Investigational Product and Active Control arms (A and B) and 16 evaluable test sites from Vehicle Control arm (C) for groin and abdominal regions.

Left/Right Balance

The application will be randomized so that each treatment is used on an equal number of left and right sides of the body.

Site and Sample Time Balance

Each groin and abdomen sample site is divided into four areas and three of the areas will be sampled – one at baseline, one at 10 minutes, and one at 6 hours. The remaining area will not be used. Therefore, for any groin or abdomen site there are 24 possible sampling orders.

The number of subjects required for a completely balanced block design for all factors at once is dependent on the ratio of the number of anatomical sites used in the active treatments compared to the number of anatomical sites used in the Vehicle Control treatment but is in any case a multiple of 48 (a factor of two for left/right balance times a factor of 24 for sample order balance). The exact subject numbers and Active/Vehicle Control ratio may make it infeasible to provide a completely balanced block design, so the following priority order will be used for design:

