14.0 ASSESSMENT OF SAFETY

14.1 **Safety Assessments**

The subject's safety will be monitored by evaluations of reactions observed on the skin of the test sites and any adverse reactions. Adverse reactions will be documented per BSLI Standard Operating Procedure, reported as an Adverse Event, and followed to resolution.

14.2 **Evaluation of Test Sites**

Prior to product application and before any subsequent samples, test site erythema, edema, rash, and dryness will be rated on a 4-step scale, the Skin Irritation Scoring System (Draize). If a subject receives a score of 1 for erythema, edema, rash, and/or dryness prior to Screening Baseline Day or product application on Treatment Day, they will be dismissed from testing. If a subject receives a score of 3 for erythema, edema, rash, and/or dryness at any point in the study, they will be dismissed from testing and reported as an adverse event. (Note: Skin irritation scores of 1 or 2 are expected after sampling and product application procedures and are not grounds for dismissal and will not be considered adverse events.)

SKIN IRRITATION SCORING SYSTEM (Draize)

	0	No reaction
E 41	1	Mild and/or transient redness limited to sensitive area
Erythema	2	Moderate redness persisting over much of the product-exposed area
	3 *	Severe redness extending over most or all of the product-exposed area
	0	No reaction
17.1	1	Mild and/or transient swelling limited to sensitive area
Edema	2	Moderate swelling persisting over much of the product-exposed area
	3 *	Severe swelling extending over most or all of the product-exposed
0		No reaction
Rash	1	Mild and/or transient rash limited to sensitive area
Rasn	2	Moderate rash persisting over much of the product-exposed area
	3 *	Severe rash extending over most or all of the product-exposed area
0 No reaction 1 Mild and/or tr		No reaction
		Mild and/or transient dryness limited to sensitive area
Dryness	2	Moderate dryness persisting over much of the product-exposed area
	3 *	Severe dryness extending over most of all of the product-exposed area

^{*} A score of 3 in one or more of the conditions evaluated represents significant irritation and qualifies as an Adverse Event.

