15.0 STATISTICAL METHODS

Data processing and statistical analysis for this study will be conducted by the BD statistical group based on the final monitored data provided by the Testing Facility to the BD statistical group.

Details of the statistical analysis will be provided in a separate statistical analysis plan.

Data sets analyzed

The full intent to treat (ITT) data set (all randomized subjects) will be used for the safety analysis.

A modified Intent to Treat (mITT) data set will be used for efficacy analyses. Inclusion for the mITT data set is evaluated for each body area (left and right for the groin and abdomen). For each body area, if the treatment day baseline bacterial count requirements are in the range of 3.11 to 5.50 log₁₀/cm², inclusive, on the abdomen and 5.50 to 7.50 log₁₀/cm², inclusive, on the groin, then the data from that body area are included in the mITT data set. Efficacy analyses will also be conducted on the Per Protocol data set as supportive analyses when Per Protocol data are different from mITT data.

- For responder rate, missing data will be treated as non-responders in the mITT data, while in the Per Protocol data, missing data will not be imputed and will be excluded from the responder rate Per Protocol analysis.
- For log reduction, missing data will not be imputed for either mITT data or Per Protocol data and will be excluded from log reduction analysis.

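### Should a site lost because the opposite product caused a score of 3 still count as a non-response in the mITT responder rate?

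*Combined protocol and SAP*

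**What the plan says.** Section 13.3 sets the split-body design: "Each subject will receive two different treatments, one on the right side of the body and one on the left". Of the minimum 56 evaluable subjects, 40 receive the Investigational Product (IP) on one side and the Active Control (AC) on the other. Eight pair IP with the Vehicle Control (VC), and eight pair AC with VC.

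Section 14.2 fixes when the skin is scored: "Prior to product application and before any subsequent samples, test site erythema, edema, rash, and dryness will be rated". For a subject who scores 3 it adds: "at any point in the study, they will be dismissed from testing and reported as an adverse event". The subject is dismissed, not the site.

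Section 7.1 admits a site to the mITT set on its Treatment Day baseline count alone. It then says: "For responder rate, missing data will be imputed as non-responders in the mITT data". Section 15.0 repeats the rule: "missing data will be treated as non-responders in the mITT data". Neither place distinguishes reasons for missingness. Both sections exclude missing results from the Per Protocol responder analysis, and from the log-reduction analyses in both data sets.

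Section 15.0 also states: "Details of the statistical analysis will be provided in a separate statistical analysis plan". That plan is not among the documents reviewed. Section 15.1 gives the 6-hour criterion: "Success at 6 hours is defined as having skin flora counts that are less than the baseline skin flora counts". On the 70% standard it accepts that "the confidence intervals may not lie entirely above 70" percent.

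**The concern.** Counting a missing result as a failure is easy to defend when the product itself caused the loss. It is harder to defend when the cause was the other product, on the other side of the body. Section 14.3 attributes adverse events to the product at the affected skin site, but the imputation rule makes no use of that information.

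The design also concentrates the effect, because 40 of the 48 IP sites (83%) lie opposite AC. A score of 3 from AC before the 6-hour sample leaves IP's 6-hour sites in mITT as failures, in every region for which that subject was admitted. The 10-minute sample is affected only if the score of 3 has already appeared by then.

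At stake is the primary measure, the IP responder rate read against 70%, and through it the figures that will inform Phase 3. For IP against VC, dismissals caused by IP could also lower the VC rate and so flatter IP.

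**Working it through.** **Design figures (13.3).** Subjects: 40 + 8 + 8 = 56. IP sites: 40 + 8 = 48. AC sites: 40 + 8 = 48. VC sites: 8 + 8 = 16. Total per region: 2 × 56 = 112. All agree with the protocol.

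**Cost per lost would-be responder.** IP or AC: 1/48 = 2.1 points. VC: 1/16 = 6.25 points. Reaching 70% of 48 takes 34 responders (34/48 = 70.8%). From 48 responders it would take 15 such losses to miss the target; from 36 (75%) it would take 3.

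**Assumptions.** The documents give no score-3 rate and no expected responder rate. Let q be the proportion of the 40 IP+AC subjects dismissed for an AC-side score of 3 before the sample, and p the true IP responder rate. Dismissal is taken as independent of IP response, sites as independent, and the IP denominator as fixed at 48. Expected IP losses are 40q: 0.4, 0.8, 2 and 4 sites for q = 1%, 2%, 5% and 10%.

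**Chance of at least 34 of 48**, with responders = Bin(40, p(1 − q)) + Bin(8, p):

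| p | q = 0 | 1% | 2% | 5% | 10% |
|---|---|---|---|---|---|
| 75% | 0.800 | 0.770 | 0.739 | 0.634 | 0.446 |
| 80% | 0.956 | 0.944 | 0.929 | 0.869 | 0.717 |
| 85% | 0.997 | 0.995 | 0.992 | 0.976 | 0.910 |
| 90% | 1.000 | 1.000 | 1.000 | 0.999 | 0.986 |

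**Break-even.** The expected IP rate is p(40(1 − q) + 8)/48. It falls below 70% only when q exceeds (1 − 0.70/p)(48/40), which is 8%, 15%, 21% and 27% for p = 75%, 80%, 85% and 90%.

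**What the planned analyses would show.** Suppose 36 of 48 IP sites would respond and two of those are lost to AC-side dismissals. The mITT rate is 34/48 = 70.8%. Excluding the two sites gives 34/46 = 73.9%. If no other IP result is missing or dropped, the Per Protocol analysis also gives 34/46.

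**IP against VC.** An IP-side dismissal costs VC on average (8/48)(1/16) = 1.04 points, in IP's favour, if the VC site would have responded. An AC-side dismissal costs VC the same 1.04 points on average and costs IP (40/48)(1/48) = 1.74 points, if the lost sites would have responded. The pulls oppose each other, so no overall direction can be claimed.

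**The case for a change.** The best case for a change is that it would be cheap and principled. One sentence in 7.1 and 15.0 could drop site-times missing solely because of a score of 3 on the opposite product's side, with the present rule kept as a sensitivity analysis. Fixing this before data are seen would avoid a later argument. The Per Protocol analysis is only supportive, and because it excludes every missing result it also forgives losses that a product brought on itself. Section 14.4 does foresee heavy erythema or swelling in some cases, so the event is possible.

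The mechanism and the lack of a stated exception stand. The case for altering the primary rule does not, for four reasons.

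- **Bias risk.** The exception removes sites because of a post-treatment event and would raise, or leave unchanged, the observed IP rate. Section 13.9 commits only to blinding those who process samples and count plates, so a skin rater may know which side received AC.
- **Selectivity.** Voluntary withdrawal also removes both sides and would still count as failure. A score of 3 in the groin would still fail the same product's abdominal site, although rates are read by region.
- **Plausibility.** Section 14.2 treats scores of 1 or 2 after application as expected and 3 as significant irritation. Known chlorhexidine or octenidine sensitivity and any pre-application score of 1 are grounds for exclusion. At 6 hours, where most of the loss would fall, any reduction counts as a response, so a true rate near 75% is the unfavourable case.
- **Limited use of the comparison.** The stated goal of a higher responder rate than VC is for 10 minutes only (7.2, 15.2), the time point least exposed.

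**Conclusion.** No change is needed. Missing as non-responder is a conservative primary rule that can hide IP success against 70% but cannot create it. The mITT and Per Protocol rates largely bracket the answer (70.8% and 73.9% in the example), and the log-reduction analyses are untouched by the imputation. The study has no power calculation, and Section 15.1 treats the 70% comparison descriptively, so no formal decision turns on a site or two.

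The size is at most 2.1 points per lost would-be responder for IP or AC and 6.25 for VC. It would be smaller if dismissed subjects are replaced to reach the evaluable minimum; the protocol does not define evaluable, so this is open. The conclusion rests on score-3 reactions being uncommon or the true rate being well above 70%; the documents give neither figure. If several one-sided score-3 dismissals did occur, the site-level irritation scores already collected would let analysts show their effect beside the planned results. The separate statistical analysis plan may already cover the case.
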